1.4.1. Dose Rationale

1.4.1.1. Carfilzomib Dose Rationale

Data suggest that carfilzomib as a single agent can produce substantial response rates in myeloma subjects across a variety of dosing cohorts. Responses were seen over a wide therapeutic window, from 15 to 70 mg/m^2 . Maximum proteasome inhibition was seen at doses 11 mg/m^2 and higher in whole blood samples taken 1 hour after the first dose. Carfilzomib is rapidly cleared from plasma with an elimination half-life of < 60 minutes at the 20 mg/m^2 dose. Large, single arm studies of the 27 mg/m^2 dose have demonstrated that this dose is very well tolerated with subjects being treated for >10 cycles without cumulative toxicities.

Carfilzomib is currently approved by the FDA in combination with lenalidomide and dexamethasone for the treatment of subjects with relapsed multiple myeloma who have received one to three prior lines of therapy. The recommended dose is $20 \, \mathrm{mg/m^2}$ on cycle 1 day 1 and can be escalated to $27 \, \mathrm{mg/m^2}$ on day 8 of cycle 1 on twice weekly schedule, i.e. on days 1, 2, 8, 9, 15, 16 in 28-day cycles. At this time, the MTD had not been defined but the dose of 36 $\, \mathrm{mg/m^2}$ on the same schedule was established as tolerated in newly diagnosed myeloma (Jakubowiak et al., 2012b; Jakubowiak, 2016; Korde et al., 2015).

In the past year, an alternative schedule of carfilzomib with weekly infusion on days 1, 8, 15 in 28-days cycles was evaluated in several studies. A number of already published as well as ongoing

evaluations reported the MTD of carfilzomib at 70mg/m² given once weekly in combinations (Berenson et al., 2016). Additionally, this weekly dose of carfilzomib was formally evaluated versus original twice-weekly schedule in the randomized ARROW trial, which completed enrollment with results still pending. Finally, the KRd+Daratumumab arm of the ongoing Janssen MMY1001 trial completed enrollment using weekly dosing of carfilzomib with 70mg/m² per dose in combination with lenalidomide, dexamethasone, and daratumumab.

1.5. Elotuzumab Background

Elotuzumab (HuLuc63/BMS-901608) is a humanized monoclonal IgG1 antibody product directed to human CS1 (CD2 subset-1, also known as CRACC and SLAMF7), a cell surface glycoprotein with homology to the CD2 family of cell surface proteins (Boles and Mathew, 2001; Tassi and Colonna, 2005). Originally, CS1 was identified as a natural killer cell (NK) marker and was shown to be expressed in a subset of circulating leukocytes (Boles et al., 2001). Blood analysis confirmed expression of CS1 on the cell surface of NK, NK-like T-cells (NKT), activated monocytes, CD8 positive T cells, and on tissue plasma cells (Hsi et al., 2008). High CS1 expression was seen in plasma cells obtained from normal healthy donors and from subjects with MGUS, SMM, and active MM. More than 90% of MM bone marrow samples, irrespective of cytogenetic abnormalities, express CS1. In addition CS1 expression is maintained in MM subjects after relapse from therapy. A paired analysis of a subset of subjects with MM showed that CS1 gene expression is detectable in subjects both at diagnosis and at relapse.

In agreement with the gene chip data, flow cytometry analysis demonstrated that CD138+ plasma cells from MM bone marrow stained strongly positive for elotuzumab binding. In addition, immunohistochemistry (IHC) using anti-CS1 antibodies showed strong staining of MM cells in 9/9 plasmacytoma tissue samples and in 20/20 myeloma bone marrow cores tested (Hsi et al., 2008) The proposed mechanism of action of elotuzumab involves natural killer (NK) cell mediated antibody dependent cell-mediated cytotoxicity (ADCC). Elotuzumab monotherapy can kill MM cell lines and primary myeloma cells in vitro in the presence of peripheral blood mononuclear cells (PBMCs) or purified NK cells. In addition, elotuzumab exhibits significant in vivo monotherapy anti-tumor activity against human myeloma xenograft models grown in severe combined immunodeficient (SCID) mice (Hsi et al., 2008; Tai et al., 2008). This in vivo anti-tumor activity of elotuzumab appears to be largely dependent on the presence of active NK cells. Experiments using an in vivo mouse xenograft model suggest that maximal antitumor activity is reached at elotuzumab serum levels of 70 to 430 mcg/mL.

Indications and Usage: Elotuzumab (EMPLICITI®) is a SLAMF7-directed immunostimulatory antibody indicated in combination with lenalidomide and dexamethasone for the treatment of subjects with multiple myeloma who have received one to three prior therapies. More details can be found on the package insert and in the Investigator Brochure.

Dosage and Administration:

- With lenalidomide and dexamethasone: 10 mg/kg administered intravenously every week for the first two cycles and every 2 weeks thereafter until disease progression or unacceptable toxicity.
- Pre-medicate with dexamethasone, diphenhydramine, ranitidine and acetaminophen

Adverse Reactions: Most common adverse reactions (20% or higher) are fatigue, diarrhea, pyrexia, constipation, cough, peripheral neuropathy, nasopharyngitis, upper respiratory tract infection, decreased appetite, pneumonia.

Complete and updated adverse events are available in the package insert.

1.5.1.1. Infusion Reactions

Elotuzumab can cause infusion reactions. Infusion reactions were reported in approximately 10% of subjects treated with elotuzumab with lenalidomide and dexamethasone in the randomized trial in multiple myeloma. All reports of infusion reaction were Grade 3 or lower. Grade 3 infusion reactions occurred in 1% of subjects. The most common symptoms of an infusion reaction included fever, chills, and hypertension. Bradycardia and hypotension also developed during infusions.

In the trial, 5% of subjects required interruption of the administration of elotuzumab for a median of 25 minutes due to infusion reactions, and 1% of subjects discontinued due to infusion reactions. Of the subjects who experienced an infusion reaction, 70% (23/33) had them during the first dose.

Administer premedication consisting of dexamethasone, antihistamines (H1 and H2 blockers) and acetaminophen prior to elotuzumab infusion (See section 6.5.2)

Interrupt elotuzumab infusion for Grade 2 or higher infusion reactions and institute appropriate medical management (See section 6.5.2).

1.5.1.2. Overall Risk/Benefit Assessment

Elotuzumab is a humanized monoclonal IgG1 antibody directed to human CS1, a cell surface glycoprotein. CS1 is expressed on plasma cells and a subset of circulating leukocytes. Since elotuzumab does not recognize non-human CS1, minimal animal toxicology has been performed. Non-clinical activity as monotherapy as well as in combination led to human trials. Although as monotherapy in heavily pretreated subject the best responses were SD, elotuzumab showed high response rates in combination with bortezomib or lenalidomide.

Elotuzumab was approved in November of 2015 for treatment of relapsed MM subjects with prior 1-3 lines of therapy. Please refer to the package insert and Investigator's Brochure for more information.

1.6. Study Rationale

Previous studies have indicated that the KRd combination (formerly CRd) is highly active in new myeloma; best response for all subjects on ITT (N=53) 98% PR, 87% VGPR, 72% \(\) nCR, 64% CR, 55% sCR, and 51% MRD-negative rate, 3-year PFS of 79% (Jakubowiak, 2016) and is well tolerated in both new myeloma (Jakubowiak, 2016) as well is in relapsed myeloma (Stewart et al., 2015). Additionally, the combination of elotuzumab with lenalidomide and dexamethasone is more active than Rd and well tolerated in relapsed MM with no significant added or overlapping toxicity after an addition of elotuzumab (Lonial et al., 2015; Moreau, 2012; Moreau et al., 2012). Finally, the combination of elotuzumab with proteasome inhibitor (bortezomib) shows encouraging activity suggestive of additive effect and no significant overlapping toxicity (Jakubowiak et al., 2012a). We hypothesize that an addition of elotuzumab to KRd combination (E-KRd combination), which includes both proteasome inhibitor (carfilzomib), and immunomodulatory drug (lenalidomide) will further improve treatment outcome, including the rate of CR/sCR and rate of MRD-negative disease.

As recently reported, incorporation of autologous stem cell transplant into KRd treatment of newly diagnosed myeloma improves rates of CR and MRD-negative disease, and appears to further improve PFS (Jakubowiak, 2016) providing, as a proof of concept, evidence that KRd results can further be improved. Since the achievement of CR and MRD negative status is associated with improved long term-control of the disease (Dytfeld et al., 2011; Harousseau et al., 2010), and elotuzumab in particular improves time to event in combination with IMiD and PI, this regimen may further improve overall treatment outcome in myeloma.

We hypothesize that treatment with E-KRd will improve the rate of sCR and/or the rate of negative MRD by next generation gene sequencing (NGS) by clonoSEQ (Adaptive Biotechnologies) at the end of 8 cycles among non-transplant candidates or transplant candidates who agreed to defer transplant compared to historical results of KRd alone. We would like to investigate this in the proposed study, in subjects who are newly diagnosed and who are transplant ineligible or those who are transplant-eligible, and choose to delay transplant. The primary efficacy endpoint will be the rate of sCR and/or the rate of negative MRD by NGS at the end of 8 cycles among non-transplant candidates and/or transplant candidates who agreed to defer transplant.

Among secondary objectives, we propose to evaluate the status of MRD disease at established landmark time-points, and to use MRD status to determine the duration of E-KRd treatment. We anticipate that E-KRd treatment will result in a statistically improved rate of MRD-negative disease compared to the MRD rate observed in subjects who were treated with KRd in the historical trial.

Based on the results from the IMF study (Avet-Loiseau et al., 2015) we propose to use different durations of E-KRd treatment using MRD status as the modifying criteria. There will be 3 possible outcomes:

- 1) Subjects who have MRD-negative disease at the completion of 8 and 12 cycles of E-KRd will receive a shorter duration of E-KRd treatment (for a total of 12 cycles) and continue on E-Rd maintenance until disease progression.
- 2) Subjects that are MRD-positive after cycle 8 but transform to MRD-negative after 12 cycles of E-KRd will receive an additional 6 cycles of E-KRd and then continue on E-Rd maintenance until disease progression.
- 3) Subjects that are MRD-positive after 8 and 12 cycles, will receive an additional 12 cycles of E-KRd and then continue on E-Rd maintenance until disease progression.

To make safety the highest priority, the protocol will (1) incorporate scheduled dose reductions of dexamethasone and will (2) provide aggressive required dose modifications with the emergence of any treatment related toxicities greater than G1.

1.7. Study Population and Sample Size

A total of 40, non-transplant candidates, and/or transplant candidates who agreed to defer transplant will be enrolled. Since the study does not plan to exclude transplant candidates who do not wish to defer transplant, additional 15 subjects who discontinue E-KRd treatment and proceed to transplant are planned to be enrolled to generate additional tolerability and toxicity data, bringing the total number of subjects to be enrolled to 55. Subjects that continue to transplant will be removed from the study and censored at the end of 4 cycles. These subjects will not be followed up or further analyzed. Intention to go on ASCT will be required at the time of enrollment with 15 subjects planned in this category per study design. Subjects who were assigned to the 'non-ASCT' or 'deferred ASCT' category who proceed to ASCT for reasons other than disease progression or toxicity, will be replaced (up to 5 subjects).

For 40 non-transplant candidates and/or transplant candidates who agreed to defer transplant, we hypothesize that treatment with E-KRd will improve the rate of sCR at the end of 8 cycles among non-transplant candidates or transplant candidates who agreed to defer transplant compared to historical results of KRd alone.

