20mg PO weekly. On days when dexamethasone and elotuzumab coincide, dexamethasone should be taken no more than 3 hours prior to elotuzumab infusion

Duration of Treatment

Cycles 1 through 4 are considered E-KRd induction cycles, cycle 5-8 E-KRd consolidation, and cycles 9+ E-KRd maintenance cycles. After Cycle 4, subjects who are deemed candidates for ASCT will proceed to stem cell harvest as per institutional guidelines. However, the study design recommends a "delayed" transplant for ASCT candidates as in completed frontline KRd study with delayed transplant for transplant candidates (Jakubowiak et al., 2012b). After completion of stem cell harvest, subjects will resume protocol treatment. Subjects who will proceed to transplant will be discontinued from the trial. Intention to go on ASCT will be required at the time of enrollment with 15 subjects planned in this category per study design. Subjects who were assigned to the 'non-ASCT' or 'deferred ASCT' category, who proceed to ASCT for reasons other than disease progression or toxicity, will be replaced (up to 5 subjects).

Subjects who will continue E-KRd protocol treatment until the end of study or toxicity, will then proceed to maintenance treatment with E-Rd, i.e. with elotuzumab (every 4 weeks), lenalidomide (days 1-21), and low dose dexamethasone (weekly) at last tolerated doses in 28-day cycles until subject reaches PD.

Inclusion / Exclusion Criteria

Inclusion criteria:

Subjects must meet all of the following inclusion criteria to be eligible to enroll in this study. No enrollment waivers will be granted.

- 1. Newly diagnosed, previously untreated myeloma requiring systemic chemotherapy
 - a. Prior treatment of hypercalcemia or spinal cord compression or active and/or aggressively progressing myeloma with corticosteroids and/or lenalidomide and/or bortezomib/PI-based regimens does not disqualify the subject. The corticosteroid treatment dose should not exceed the equivalent of 160 mg of dexamethasone in a 4 week period or not more than 1 cycle of lenalidomide and/or PI-based therapy. A higher total dose of corticosteroid is allowed for the management of cord compression at the discretion of the PI, as long as the subject does not exhibit any steroid related toxicities at the initiation of study treatment.
- 2. Both transplant and non-transplant candidates are eligible.
- 3. Diagnosis of symptomatic multiple myeloma as per current IMWG uniform criteria prior to initial treatment

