10.2. Sample Size Justification & Analysis Plan

A total of 40, non-transplant candidates, and/or transplant candidates who agreed to defer transplant will be enrolled. Since the study does not plan to exclude transplant candidates who do not wish to defer transplant, an additional 15 subjects who discontinue E-KRd treatment and proceed to transplant are planned to be enrolled to generate additional tolerability and toxicity data, which will bring a total number of subjects to be enrolled to 55. Subjects that continue to transplant will be removed from the study and censored at the end of 4 cycles. These subjects will not be followed up or further analyzed

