10.2.1. Primary Objective Sample Size Justification

The primary endpoint is the sCR rate and/or the rate of MRD-negativity after 8 cycles of therapy. The rate of sCR for KRd treatment is established as the primary reference endpoint for statistical considerations by robust data (Jakubowiak et al., 2012b) Recognizing that the measurement of sCR has technical challenges when involving elotuzumab – which are anticipated to be resolved by the time it is needed – a co-primary endpoint of MRD-negative status by NGS is included in the primary efficacy assessment. This is based on the close correlation between MRD-negative status and sCR rate established in the ongoing KRd+transplant study (Jakubowiak et al. EHA 2016, Zimmerman et al. ASH 2016, both oral presentations). This primary endpoint incorporates also the new definition of MRD status, which requires sCR to confirm MRD negativity (Kumar et al., 2016). Therefore, an improvement from historical 30% (which is the sCR rate and the estimated MRD-negative rate by NGS in the KRd study without elotuzumab (Jakubowiak, 2016)) to 50% or higher sCR and/or MRD-negative status at the completion of 8 cycles, would be considered promising.

For 40 non-transplant candidates and/or transplant candidates who agreed to defer transplant, we will test the null hypothesis that the sCR and/or negative MRD status by NGS rate after 8 cycles is, \leq 30% against the alternative that it is, \geq 30% using an exact one-sided binomial test at the alpha=0.10 significance level. The null hypothesis will be rejected if 17 or more sCR's and/or MRD-negative's responses are observed (\geq 42.5%). The sample size of n=40 response evaluable subjects provides a little over 85% power if the true sCR and/or negative MRD status rate by NGS is 50%. The sample size is selected to also allow for collection of sufficient data for toxicity and tolerability evaluation of the E-KRd regimen. The frequency of adverse events will be summarized by type, grade, and attribution to the study drugs.

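### Up to 5 deferred or non-ASCT subjects who leave for transplant can be replaced, and the plan does not say how the primary cycle-8 test counts them; if they leave because of poor response, the one-sided error rate could rise from 0.063 to at most 0.164.

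*Combined protocol and SAP*

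**What the plan says.** The primary cohort is 40 subjects who either are not transplant candidates or have agreed to defer transplant (sections 1.7 and 10.2). A further 15 subjects who intend transplant are enrolled for tolerability data. Intention to have ASCT is required at enrolment.

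On departures:
- Section 1.7, and the Synopsis under Duration of Treatment, say that subjects assigned to the non-ASCT or deferred-ASCT category "who proceed to ASCT for reasons other than disease progression or toxicity, will be replaced (up to 5 subjects").
- The same part of the Synopsis states: "Subjects who will proceed to transplant will be discontinued from the trial".
- Sections 1.7 and 10.2 remove subjects who go on to transplant and censor them at the end of cycle 4. Section 10.2 adds: "These subjects will not be followed up or further analyzed".

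On the test, section 10.2.1 compares a 30% null rate with a 50% target "using an exact one-sided binomial test at the alpha=0.10 significance level". It continues: "The null hypothesis will be rejected if 17 or more sCR's and/or MRD-negative's responses are observed", and "The sample size of n=40 response evaluable subjects provides a little over 85% power".

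The only reference to an intention-to-treat analysis is in section 6.6. It concerns stopping a study drug before the end of cycle 8, and the set is not defined. Section 10.2.2 includes transplant subjects in the cycle-4 sCR test and bases PFS, TTP and OS on everyone dosed.

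**The concern.** The cut-off of 17 assumes 40 subjects who were not selected on outcome. The replacement rule excepts only progression and toxicity. A subject with a shallow but non-progressing response who opts for transplant can therefore be exchanged for a new one.

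The circumstances make this plausible. The trial is open-label, M-protein is assessed every cycle (sections 4.2 and 6.2.2), marrow is taken at the end of cycle 4 (6.2.2), and stem cell harvest follows cycle 4 (Synopsis). Section 1.6 reports that adding transplant to KRd improves CR and MRD-negative rates, which gives a reason to choose it after a shallow response.

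If such subjects leave the primary denominator, the observed rate rises without any drug effect. A single-arm trial has no concurrent control to reveal this.

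**Working it through.** **Inputs.** Null rate 0.30, target 0.50, one-sided alpha 0.10, n = 40, cut-off 17 (section 10.2.1). Replacement cap 5 (section 1.7). Historical sCR 8% at the end of cycle 4 (section 10.2.2) and 30% after 8 cycles (section 10.2.1). The number of leavers and their would-be response rate are not in the documents, so they are assumptions shown as a range.

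**Step 1: the plan's own figures.** P(Bin(40, 0.30) ≥ 17) = 0.063 and P(Bin(40, 0.50) ≥ 17) = 0.866, which agrees with the stated power of a little over 85%. A cut-off of 16 would give 0.115, so 17 is the correct exact cut-off for n = 40.

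**Step 2: worst case.** Suppose k replaced subjects would all have been non-responders. The responders among the 40 analysed then equal the responders among all 40 + k enrolled, so the true error rate is P(Bin(40 + k, 0.30) ≥ 17):

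| k replaced | Error rate |
|---|---|
| 0 | 0.063 |
| 1 | 0.079 |
| 2 | 0.097 |
| 3 | 0.117 |
| 4 | 0.139 |
| 5 | 0.164 |

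With 1 or 2 replaced, 0.10 is not reached even in this worst case.

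**Step 3: leavers who might have responded.** Let the k leavers have would-be response rate q. Holding the overall rate at 30%, the retained 40 respond at p = (0.30(40 + k) − kq)/40, and the error rate is approximately P(Bin(40, p) ≥ 17):

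| k | q = 0 | q = 0.05 | q = 0.10 | q = 0.15 | q = 0.20 |
|---|---|---|---|---|---|
| 3 | 0.113 | 0.103 | 0.094 | 0.086 | 0.078 |
| 4 | 0.134 | 0.120 | 0.107 | 0.094 | 0.083 |
| 5 | 0.158 | 0.138 | 0.120 | 0.103 | 0.089 |

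At q = 0 this approximation is slightly below the exact values of step 2. With all 5 replaced, the error rate falls to 0.10 at q of about 0.16: p = (13.5 − 0.8)/40 = 0.3175, giving 0.100.

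**Step 4: what the protocol's historical rates imply for q.** If cycle-4 sCRs persist, a subject not yet in sCR at cycle 4 reaches it by cycle 8 with probability (0.30 − 0.08)/(1 − 0.08) = 0.24. With k = 5, p = (13.5 − 1.2)/40 = 0.3075 and the error rate is 0.078.

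**Step 5: the rate of leaving as the assumption.** In a simulation (200,000 runs), each non-responder leaves with probability d, the first 5 leavers are replaced and later ones count as failures. The error rate is 0.085 at d = 5%, 0.110 at 10%, 0.133 at 15%, 0.150 at 20% and 0.162 at 30%. If responders and non-responders leave equally often (5% to 15%), it is 0.064 to 0.042, so there is no inflation.

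**Step 6: counting everyone.** With leavers kept as non-responders, the exact cut-offs at alpha ≤ 0.10 are:

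| Final n | Cut-off | Alpha |
|---|---|---|
| 40 | 17 | 0.063 |
| 41 | 17 | 0.079 |
| 42 | 17 | 0.097 |
| 43 | 18 | 0.066 |
| 44 | 18 | 0.081 |
| 45 | 18 | 0.099 |

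At n = 45 the power is 0.932 if 50% of all 45 respond on study. If instead 3 to 5 leavers are unrelated to response and the retained 40 respond at 50%, power is P(Bin(40, 0.50) ≥ 18) = 0.785.

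**The case against.** The documents nowhere name poor cycle-4 response as a reason for crossing to transplant, and they forecast no crossovers. Part of the cohort are not transplant candidates and are unlikely to cross at all. Not being in sCR at cycle 4 is the normal course of a later responder: on the protocol's own 8% and 30%, the average such subject still reaches sCR about 24% of the time. Inflation past 0.10 therefore needs leavers clearly worse than that average and at least 3 of the 5 replacements.

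The endpoint measures are also partly unavailable at that point. Cycle-4 NGS samples are shipped in batches, with only cycle 12 sent direct (section 7), and the interference assay is not for clinical decisions (section 1.8). All of this stands. It lowers the likelihood of the bias but does not remove it, because conventional M-protein and marrow results remain available.

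Two stronger readings are tempting. First, a reader might infer that the plan expressly excludes replaced subjects from the primary rate. It does not: the no-further-analysis sentence directly follows the text on the 15 transplant-intent subjects, and section 10.2 omits the replacement rule. The supportable statement is that nothing keeps replaced subjects in the denominator. They are also not lost to every analysis, given section 10.2.2. Second, a reader might infer that transplant-intent subjects with deep responses could be moved into the primary cohort. No text provides for that, and section 1.7 requires the intention at enrolment.

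**Conclusion.** The concern holds as a gap in the plan. The rule permits replacement related to outcome, and the primary analysis set is undefined for replaced subjects. If those subjects are left out and departure depends on poor response, the error rate lies between 0.063 and a ceiling of 0.164 set by the cap of 5. Four or 5 replacements need not all be certain non-responders for it to pass 0.10, but their would-be response rate has to be low. It stays near 0.08 if all 5 leavers resemble the average subject not yet in sCR at cycle 4, and there is no inflation if departure is unrelated to response.

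The documents do not support saying that the error rate will exceed 0.10, or that a positive result would be an artefact of replacement. Given the cap, the exceptions for progression and toxicity, and the attained alpha of 0.063, this is a should-fix point.

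**What to change.** In sections 1.7, 10.2 and 10.2.1:
- Define the primary cohort by the transplant category recorded at enrolment.
- Add an analysis of all treated subjects in that cohort, replaced subjects included. Count those who cross to ASCT before the end of cycle 8 as non-responders. Use a cut-off of 17 for n = 40 to 42 and 18 for n = 43 to 45.
- Report it beside the 40-subject analysis with replacements, list the reason for each crossover, and describe a positive result as robust only if both agree.

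Because leavers add no responders, the two analyses share the same responder count. They can disagree only when there are exactly 17 responders and 3 to 5 replacements.

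The change is one of wording: no subjects beyond the planned replacements and no change to treatment. Its cost is conservatism. If 3 to 5 departures are unrelated to response, the all-assigned analysis has power 0.785 at a 50% rate in the 40 retained, against the stated 85%. With 1 or 2 such departures the cut-off stays at 17 and power stays at 0.866. Reporting both analyses with the crossover reasons lets the reader judge which case applies.
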